6.3.2 Follow-up of unresolved adverse events

Any AEs that are unresolved at the patient's last AE assessment in the study are followed up by the Investigator for as long as medically indicated, but without further recording in the eCRF. AstraZeneca retains the right to request additional information for any patient with ongoing AE(s)/SAE(s) at the end of the study, if judged necessary.

6.3.3 Variables

The following variables will be collect for each AE;

- AE (verbatim)
- The date when the AE started and stopped
- Maximum intensity
- Whether the AE is serious or not
- Investigator causality rating against the study drug (yes or no)
- Action taken with regard to study drug
- AE caused patient's withdrawal from study (yes or no)
- Outcome.

In addition, the following variables will be collected for SAEs:

- Date AE met criteria for serious AE
- Date Investigator became aware of serious AE
- AE is serious due to
- Date of hospitalization
- Date of discharge
- Probable cause of death
- Date of death
- Autopsy performed
- Causality assessment in relation to Study procedure(s)
- Causality assessment in relation to Other medication
- Description of AE.

It is important to distinguish between serious and severe AEs. Severity is a measure of intensity whereas seriousness is defined by the criteria in Section 6.2. An AE of severe intensity need not necessarily be considered serious. For example, nausea that persists for several hours may be considered severe nausea, but not a SAE unless it meets the criteria

shown in Section 6.2. On the other hand, a stroke that results in only a limited degree of disability may be considered a mild stroke but would be a SAE when it satisfies the criteria shown in Section 6.2.

Maximum intensity refers to the complete course of the AE. The patient (parents/legal guardians) will be asked to assess the maximum intensity of the reported AEs according to the following scale:

- Mild (awareness of sign or symptom, but easily tolerated)
- Moderate (discomfort sufficient to cause interference with normal activities)
- Severe (incapacitating, with inability to perform normal activities).

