The primary objective of the trial is to describe the safety profile of osimertinib in routine clinical practice and add to the limited burden of safety data on osimertinib currently available as assessed by the incidence of adverse events (AEs) (Serious and Non-serious AEs) observed during trial. Considering the epidemiology of metastatic NSCLC- adenocarcinoma subtype which are positive for EGFR sensitizing mutation and have progressed after EGFR-TKI based treatment in first line setting and prevalence of T790M-mutation after such progression, a sample size of 60 patients is expected to provide the following exact two sided 95% confidence interval for a list of percentages of patients reporting at least one AE (Julious and Campbell 2012).

Observed rate expressed as % (number of patients reporting at least one AE*)	Lower Limit of CI (%)	Upper Limit of CI (%)
0%	0	6.0
1%	0	7.8
2%	0.1	9.5
5%	1.0	13.9
10%	3.8	20.5
20%	10.8	32.3
30%	18.8	43.2
40%	27.6	53.5
50%	36.8	63.2

^{*}the symptom could be any of the expected AE, unexpected AE or SAE. The calculation is based on the link between binomial and beta distributions.

Hypothesis

No formal hypothesis testing will be conducted.

Statistical Analysis

Data will be summarized using descriptive statistics. Continuous variables will be summarized using the number of observations, mean, SD, coefficient of variation, median, and range as appropriate. Categorical values will be summarized using the number of observations and percentages as appropriate. Shift tables will be provided to determine the change in reported outcomes from baseline.

The safety analysis population will include all patients who sign the ICF and receive at least one dose of osimertinib.

Adverse Events (both in terms of MedDRA preferred terms and CTCAE grade) will be listed individually by patient. Any AE occurring before treatment with osimertinib will be included in the data listings but will not be included in the summary tables of AEs.

Any AE occurring within 28 days of discontinuation of study drug (ie, the last dose of osimertinib) will be included in the AE summaries. Any events in this period that occur after a patient has received further therapy for cancer (following discontinuation of osimertinib) will be flagged in the data listings.

TIME AND EVENTS SCHEDULE

Table 1. Time and Event Schedule

Study Phase	Screening Phase ^(a)	Treatment Phase		Follow-up Phase
Cycle	1 muse	Cycles 1-6	EOT	EOS

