6.3.6 Adverse events based on examinations and tests

The results from protocol mandated laboratory tests, vital signs and other safety assessments will be summarized in the CSR. Deterioration as compared to baseline in these parameters will therefore only be reported as AEs if they fulfil any of the SAE criteria or are the reason for discontinuation of treatment with the study drug.

If deterioration in a laboratory value, vital sign or other safety assessment is associated with clinical signs and symptoms, the sign or symptom will be reported as an AE and the associated laboratory result or other finding will be considered as additional information. In the absence of clinical signs and symptoms, clinically relevant deteriorations in non-mandated parameters should be reported as AE(s).

Any new or aggravated clinically relevant abnormal medical finding at a physical examination as compared with the baseline assessment will be reported as an AE.

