8.5.1 Analysis of the primary variable (s)

Adverse Events

The verbatim terms used in the CRF by investigators to identify adverse events will be coded using the Medical Dictionary for Regulatory Activities (MedDRA) and CTCAE grade and will be listed individually by patient. Treatment-emergent adverse events are adverse events with onset during the treatment phase or that are a consequence of a pre-existing condition that has worsened since baseline. All reported adverse events will be included in the analysis. For each adverse event, the percentage of subjects who experience at least 1 occurrence of the given event will be summarized.

Any AE occurring before treatment with osimertinib will be included in the data listings but will not be included in the summary tables of AEs. Any AE occurring within 28 days of discontinuation of investigational product (ie, the last dose of osimertinib) will be included in the AE summaries.

Any events in this period that occur after a patient has received further therapy for cancer (following discontinuation of osimertinib) will be flagged in the data listings.

Adverse events of special interest (for example interstitial lung disease/pneumonitis-like events; QTc prolongation events]) will be summarized separately.

Summaries, listings, datasets, or subject narratives may be provided, as appropriate, for those subjects who die, who discontinue treatment due to an adverse event, or who experience a severe or a serious adverse event.

Clinical Laboratory Tests

Laboratory data will be summarized by type of laboratory test. Descriptive statistics will be calculated for each laboratory analyte at baseline and for observed values and changes from baseline at each scheduled time point. Changes from baseline results will be presented in pre- versus posttreatment cross-tabulations (with classes for below, within, and above normal ranges). Parameters with predefined National Cancer Institute Common Terminology Criteria for Adverse Events (NCI-CTCAE) toxicity grades will be summarized. Change from baseline to the worst adverse event grade experienced by the subject during the study will be provided as shift tables. A listing of subjects with any laboratory results outside the reference ranges will be provided. A listing of subjects with any markedly abnormal laboratory results will also be provided.

Electrocardiogram (ECG)

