## 8.7 Safety Analysis

### 8.7.1 Adverse Events

All adverse events (AEs) will be coded by System Organ Class (SOC) and Preferred Term (PT) according to the Medical Dictionary for Regulatory Activities (MedDRA) Version 23.0. The intensity of adverse events is graded by the National Cancer Institute (NCI) Common Terminology Criteria for Adverse Events (CTCAE) version 4.0 or higher.

*Treatment-emergent adverse events are adverse events with onset during the treatment phase or that are a consequence of a pre-existing condition that has worsened since baseline. All reported adverse events will be*

*included in the analysis. For each adverse event, the percentage of subjects who experience at least 1 occurrence of the given event will be summarized.*

*Any AE occurring before treatment with osimertinib will be included in the data listings but will not be included in the summary tables of AEs. Any AE occurring within 28 days of discontinuation of investigational product (i.e., the last dose of osimertinib) will be included in the AE summaries.*

*Any events in this period that occur after a patient has received further therapy for cancer (following discontinuation of osimertinib) will be flagged in the data listings.*

*Adverse events of special interest (for example interstitial lung disease/pneumonitis-like events; QTc prolongation events) will be summarized separately.*

*Summaries, listings, datasets, or subject narratives may be provided, as appropriate, for those subjects who die, who discontinue treatment due to an adverse event, or who experience a severe or a serious adverse event.*

An overall summary will be provided in terms of count and percentages for:

- AEs
- TEAEs
- Grade 3 and above TEAEs
- Grade 3 and above related TEAEs
- Treatment-related TEAEs
- Treatment-related serious TEAEs
- TEAEs leading to dose change/ interruption/ discontinuation
- Treatment related TEAEs leading to dose change/ interruption/ discontinuation
- Serious TEAEs
- Fatal TEAEs
- Related Fatal TEAEs

Summaries in terms of count and percentages by SOC and PT will be provided for the following:

- TEAEs
- Treatment-Emergent SAEs
- Grade 3 and above TEAEs
- Treatment-related TEAEs
- Grade 3 and above treatment-related TEAEs
- TEAEs leading to dose change/ interruption/ discontinuation
- Adverse Events of special interest

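### Protocol 6.3.3 records adverse-event severity only on a patient-rated three-level scale, which cannot supply the SAP's four Grade 3-and-above outputs

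*Protocol*

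**What the plan says.** Protocol 6.3.3 sets out the variables recorded for every adverse event and a further list for serious ones. Severity appears once, as maximum intensity over the whole course of the event. On who rates it, the section says: "The patient (parents/legal guardians) will be asked to assess the maximum intensity of the reported AEs according to the following scale". The scale has three levels, and the lowest is described as "Mild (awareness of sign or symptom, but easily tolerated". Neither list contains a CTCAE grade or an investigator rating of severity. Causality, in the same list, is expressly assigned to the investigator.

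The other sections use CTCAE grade:

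- Protocol synopsis, Statistical Analysis: "Adverse Events (both in terms of MedDRA preferred terms and CTCAE grade) will be listed individually by patient".
- Protocol 8.5.1: verbatim terms are to be "coded using the Medical Dictionary for Regulatory Activities (MedDRA) and CTCAE grade and will be listed individually by patient".
- Protocol 6.7, Table 3 footnote a: the intensity of clinical adverse events is graded by CTCAE version 4.0, in the context of dose adjustment.
- SAP 8.7.1: "The intensity of adverse events is graded by the National Cancer Institute (NCI) Common Terminology Criteria for Adverse Events (CTCAE) version 4.0 or higher". The same section plans summaries restricted to Grade 3 and above, for example "Grade 3 and above treatment-related TEAEs".

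**The concern.** The collection section and the analysis sections name different scales. Section 6.3.3 also gives the rating to the patient, while no section says who assigns the CTCAE grade. A site that followed 6.3.3 literally would record mild, moderate or severe in the patient's judgement. The programmer of the SAP tables would then need a grade that the collection section does not provide.

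The trial's sole objective is safety, so the description of severity is a substantial part of what it reports. The stake is still limited. The primary outcome (Protocol section 2) counts patients with adverse events, serious adverse events, events of special interest and deaths, none of them defined by grade. SAP 7.1 rules out formal hypothesis testing.

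**Working it through.** **1. The plan's own figure.** The only design calculation is the table of exact 95% confidence intervals for 60 patients (Protocol 8.2, SAP 4). With x = 60 × rate, the lower limit is the 0.025 quantile of Beta(x, 60 − x + 1) and the upper limit is the 0.975 quantile of Beta(x + 1, 60 − x). At 10%, x = 6: Beta(6, 55) gives 3.76% and Beta(7, 54) gives 20.51%, against 3.8 and 20.5 in the plan. All nine rows reproduce within rounding. Nothing in this point disputes the table or changes it.

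**2. The sections side by side.**

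| Place | Severity scale | Rater | Purpose |
|---|---|---|---|
| Protocol 6.3.3 | Mild, moderate, severe | Patient | Recording each event |
| Protocol 6.7, Table 3 footnote | CTCAE 4.0 | Not stated | Dose adjustment |
| Protocol synopsis and 8.5.1 | CTCAE grade | Not stated | Listing by patient |
| SAP 8.7.1 | CTCAE 4.0 or higher | Not stated | Summary tables |

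The conflict is therefore inside the Protocol (6.3.3 against 6.7 and 8.5.1) as well as between the Protocol and the SAP.

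**3. Could another recorded item stand in for the grade?**

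- *The three-level scale itself.* No section maps it to CTCAE. Its levels are defined by the patient's awareness, discomfort or incapacity, and none is tied to the Grade 2/Grade 3 boundary that the SAP tables need.
- *Seriousness.* Section 6.3.3 itself says that severity and seriousness are different things. Seriousness criteria and outcome may flag life-threatening or fatal events, but they do not identify Grade 3.
- *Laboratory grades.* SAP 8.7.2 derives these for laboratory parameters only. Protocol 6.3.6 keeps most deteriorations in mandated laboratory tests out of the adverse-event data.
- *Grading for treatment decisions.* Protocol 3.9 and 6.7 require sites to recognise Grade 3 or higher reactions, so grades may exist in source records. Neither section makes the grade a recorded adverse-event variable.

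**4. Outputs that need the grade (SAP 8.7.1).**

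- Overall summary: 11 rows, of which 2 are Grade 3 and above (all, and related).
- Summaries by SOC and PT: 7, of which 2 are Grade 3 and above (all, and treatment-related).
- Total: 2 + 2 = 4 of 11 + 7 = 18.

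**5. Scale.** With 60 patients, one patient placed on the wrong side of Grade 3 moves a reported percentage by 1/60 = 1.67 points. This is arithmetic, not an estimate of error. The documents give no figure from which the frequency or direction of misclassification could be derived.

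**The case against.** The strongest reply is that a grade is probably collected. SAP section 1 says that the SAP was written from CRF version 1.0 as well as from the Protocol. SAP 8.7.1 states in the present tense that intensity is graded by CTCAE, and does so outside the italics that the SAP reserves for Protocol text. SAP 8.7.5 (Other Safety Parameters) also lists items such as skin reaction and ejection fraction, which neither the Time and Event Schedule nor 6.3.3 itemises. The SAP therefore appears to reflect CRF content beyond the Protocol's lists. The mention of parents in 6.3.3, in a trial of adults, suggests carried-over text.

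This largely stands. Absence from the 6.3.3 list is weak evidence that no grade was collected, and the SAP does tell a reader that its tables use CTCAE. The reply does not remove the contradiction: 6.3.3 still gives sites a different scale and a different rater, and the SAP names no source field.

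Four stronger readings are tempting, and the documents do not support them:

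- *The Grade 3-and-above tables have no valid source.* That would require knowing that the CRF holds no grade.
- *QTc prolongation must be rated by a patient who feels nothing.* The sentence "In the absence of clinical signs and symptoms, clinically relevant deteriorations in non-mandated parameters should be reported as AE(s" (Protocol 6.3.6; the closing bracket is cut off here) concerns non-mandated parameters. The 12-lead ECG is mandated in the Time and Event Schedule. Its deterioration is an adverse event only if it meets a seriousness criterion or leads to discontinuation, and where there are symptoms the symptom is what is reported. SAP 8.7.4 also tabulates QTc by numerical category.
- *Narratives will be selected on the patient's scale.* The text does cover those "who experience a severe or a serious adverse event", but it says only that narratives may be provided as appropriate. This discretionary wording is not counted as affected output.
- *CTCAE 5.0 in SAP 8.7.2 contradicts 8.7.1.* It does not. Version 5.0 applies to grades derived from laboratory values, and the 8.7.1 wording applies to adverse-event intensity.

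**Conclusion.** The point holds as a contradiction between sections. Protocol 6.3.3 specifies a rater and a scale that the Protocol's own grading text and the SAP do not use, and no conversion is given. As written, it cannot supply four of the 18 planned summary items in SAP 8.7.1.

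The effect on results depends on CRF version 1.0. If it holds a CTCAE grade, as the SAP wording suggests it may, the effect is nil and only the text is wrong. If it does not, the four outputs rest on a grading step that neither document describes, and its error cannot be sized from what is available. In either case the primary outcome definition, the sample size and the interval table are unaffected.

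**What to change.** 1. **Protocol 6.3.3:** list the investigator-assigned maximum CTCAE grade as the severity variable for each adverse event. A patient rating may be kept as a separate item, stated not to feed the Grade 3-and-above tables.
2. **SAP 8.7.1:** name that CRF field as the source of all four outputs, and replace the open-ended version wording with the single CTCAE version used for adverse events.
3. **CRF version 1.0:** check whether the grade is there. If it is not, state in the SAP how grades are assigned from the recorded data, by whom, and the limits of doing so.

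**Cost.** If the CRF already holds a grade, the change is wording only. If it does not, the main cost is retrospective grading of recorded events. The SAP cites a March 2020 drug dictionary (8.4), while the Protocol planned the last visit for 30 June 2019. On the planned dates a new field could not be filled prospectively; actual dates are not given. Sites already had to recognise Grade 3 or higher reactions under Protocol 3.9 and 6.7, so the judgement itself is not new to them. No dosing or discontinuation rule is touched.

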6.3.4 Causality collection

The Investigator will assess causal relationship between Study drug and each Adverse Event, and answer 'yes' or 'no' to the question 'Do you consider that there is a reasonable possibility that the event may have been caused by the study drug?'

For SAEs causal relationship will also be assessed for other medication and study procedures. Note that for SAEs that could be associated with any study procedure the causal relationship is implied as 'yes'.

A guide to the interpretation of the causality question is found in APPENDIX A. ADDITIONAL SAFETY INFORMATION to the Clinical Study Protocol.

6.3.5 Adverse events based on signs and symptoms

All AEs spontaneously reported by the patient or care provider or reported in response to the open question from the study personnel: 'Have you had any health problems since the previous visit/you were last asked?', or revealed by observation will be collected and recorded in the eCRF. The question will be put to each patient (or parent/legal guardian) in local language from Visit 2 to the last follow-up telephone contact. When collecting AEs, the recording of diagnoses is preferred (when possible) to recording a list of signs and symptoms. However, if a diagnosis is known and there are other signs or symptoms that are not generally part of the diagnosis, the diagnosis and each sign or symptom will be recorded separately.

6.3.6 Adverse events based on examinations and tests

The results from protocol mandated laboratory tests, vital signs and other safety assessments will be summarized in the CSR. Deterioration as compared to baseline in these parameters will therefore only be reported as AEs if they fulfil any of the SAE criteria or are the reason for discontinuation of treatment with the study drug.

If deterioration in a laboratory value, vital sign or other safety assessment is associated with clinical signs and symptoms, the sign or symptom will be reported as an AE and the associated laboratory result or other finding will be considered as additional information. In the absence of clinical signs and symptoms, clinically relevant deteriorations in non-mandated parameters should be reported as AE(s).

Any new or aggravated clinically relevant abnormal medical finding at a physical examination as compared with the baseline assessment will be reported as an AE.

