6.1 Definition of adverse events

An adverse event is the development of an undesirable medical condition or the deterioration of a pre-existing medical condition following or during exposure to a pharmaceutical product, whether or not considered causally related to the product. An undesirable medical condition can be symptoms (e.g., nausea, chest pain), signs (e.g., tachycardia, enlarged liver) or the abnormal results of an investigation (e.g., laboratory findings, electrocardiogram). In clinical studies, an AE can include an undesirable medical condition occurring at any time, including run-in or washout periods, even if no study treatment has been administered.

The term AE is used to include both serious and non-serious AEs.

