6.7 Management of study drug related toxicities

If a patient experiences a CTCAE grade 3 and/or unacceptable toxicity not attributable to the disease or disease-related processes under investigation, dosing will be interrupted and supportive therapy administered as required in accordance with local practice/guidelines.

If a toxicity resolves or reverts to ≤CTCAE grade 2 within 3 weeks of onset, treatment with study drug may be restarted at the same dose (80 mg) or a lower dose (40 mg) using the rules below for dose modifications (Table 3) and with discussion and agreement with the AstraZeneca Study Team Physician as needed. There will be no individual modifications to dosing schedule in response to toxicity, only potential dose reduction or dose interruption.

If the toxicity does not resolve to ≤CTCAE grade 2 after 3 weeks, then the patient should be withdrawn from the study and observed until resolution of the toxicity.

Table 3. OSIMERTINIB dose adjustment information for adverse reactions

Target		
organ	Adverse reaction ^a	Dose modification
Pulmonary	ILD/Pneumonitis	Permanently discontinue OSIMERTINIB
Cardiac	QTc interval greater than 500 msec on at least 2 separate ECGs	Withhold OSIMERTINIB until QTc interval is less than 481 msec or recovery to baseline if baseline QTc is greater than or equal to 481 msec, then restart at a reduced dose (40 mg)
	QTc interval prolongation with signs/symptoms of serious arrhythmia	Permanently discontinue OSIMERTINIB
Other	Grade 3 or higher adverse reaction	Withhold OSIMERTINIB for up to 3 weeks
	If Grade 3 or higher adverse reaction improves to Grade 0-2 after withholding of OSIMERTINIB for up to 3 weeks	OSIMERTINIB may be restarted at the same dose (80 mg) or a lower dose (40 mg)
	Grade 3 or higher adverse reaction that does not improve to Grade 0-2 after withholding for up to 3 weeks	Permanently discontinue OSIMERTINIB

^a Note: The intensity of clinical adverse events graded by the National Cancer Institute (NCI) Common Terminology Criteria for Adverse Events (CTCAE) version 4.0.

ECGs: Electrocardiograms; QTc: QT interval corrected for heart rate

On resolution of toxicity within 3 weeks:

• If an AE subsequently requires dose interruption, study drug may restart at the same dose or the reduced dose, on resolution/improvement of the AE at the discretion of the Investigator.

ILD/Pneumonitis-like toxicity

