8.3 Description of outcome variables in relation to objectives

Analysis will be conducted to evaluate the following as available in the CRF:

- Baseline characteristics: demographics, relevant medical history, disease characteristics, cancer treatment history.
- Exposure to the study drug
- Adverse events SAEs, AEs leading to dose modification or discontinuation, and AEs of special interest (for example interstitial lung disease/pneumonitis-like events; QTc prolongation events)
- Death due to AE, or unknown cause (except death due to disease progression).

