9.3 Data management by delegate of AstraZeneca

Data management will be performed by CRO, according to the Data Management Plan. Adverse events and medical/surgical history will be classified according to the terminology of the latest version the Medical Dictionary for Regulatory Activities (MedDRA). Medications will be classified according to the AstraZeneca Drug Dictionary. Classification coding will be performed by CRO.

Data collected will include patient demographics, information needed to determine patient eligibility (including medical history, past and current disease characteristics, and tumour EGFR mutational status), exposure of the study drug (including starting dose, dose adjustments or discontinuations), investigator-reported efficacy (including tumour response and disease progression), and safety (including SAEs, AEs leading dose-modification).

Data will be entered in the web-based data capture (WBDC) system at the Investigator's site. The Investigator (or delegate) will be responsible for entering data into the WBDC system and according to the Investigator Instructions Manual. The Investigator Instructions Manual will also provide the study site with data entry instructions. The data collected through third party sources will be obtained and reconciled against study data. Data entered in the WBDC system will be immediately saved to a central database and changes tracked to provide an audit trail. When data have been entered, reviewed and edited, the Investigator will be notified to sign the CRF electronically as per the agreed project process. A copy of the CRF will be archived at the Investigator's site.

Data queries will be raised for inconsistent, impossible or missing data. All entries to the study database will be available in an audit trail.

The data will be validated as defined in the Data Management Plan. Quality control procedures will be applied to each stage of data handling to ensure that all data are reliable and have been processed correctly. The Data Management Plan will also clarify the roles and responsibilities of the various functions and personnel involved in the data management process

When all data have been coded, validated, << signed>> and locked, clean file will be declared. Any treatment revealing data may thereafter be added and the final database will be locked.

Serious Adverse Event (SAE) Reconciliation

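### Protocol 6.3.6 gives no AE trigger to a symptom-free, non-serious ECG or laboratory finding that only interrupts or reduces dosing, so some AE rows may be slightly under-counted

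*Protocol*

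**What the plan says.** Protocol 6.3.6 sets the rule for scheduled tests: "Deterioration as compared to baseline in these parameters will therefore only be reported as AEs if they fulfil any of the SAE criteria", or if the deterioration is why study drug was discontinued. Its reason is that these results will be summarized in the study report anyway. When a finding comes with symptoms, the symptom is the AE and the test result is supporting information. For findings without symptoms it says only that "clinically relevant deteriorations in non-mandated parameters should be reported as AE(s".

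Other sections take a wider view:

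- Protocol 6.1 says that an undesirable condition can be "the abnormal results of an investigation (e.g., laboratory findings, electrocardiogram".
- Table 3 in Protocol 6.7 places "QTc interval greater than 500 msec on at least 2 separate ECGs" in its adverse-reaction column. The action is to withhold and then restart at a lower dose. Permanent discontinuation is a separate action in the same table.
- Protocol 8.3 names as outcomes "AEs leading to dose modification or discontinuation, and AEs of special interest (for example interstitial lung disease/pneumonitis-like events; QTc prolongation events". Protocol 9.3 describes the data to be collected as "safety (including SAEs, AEs leading dose-modification".
- SAP 8.7.1 plans counts and percentages for TEAEs that led to a dose change, interruption or discontinuation, for Grade 3 and above TEAEs, for treatment-related TEAEs and for events of special interest, with QTc prolongation as an example.

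**The concern.** The primary outcome in Protocol 2 is the number and proportion of patients with AEs, SAEs and events of special interest. The rule that decides what becomes an AE therefore decides what the main tables can contain. Under 6.3.6 a test-based finding that changed dosing is an AE if the drug was discontinued, but not if it was held or reduced and the patient had no symptoms.

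A site that follows 6.3.6 to the letter would record no AE for such a finding. A site that works from 6.1, or from the column heading of Table 3, might record one. For the rows named above the effect is zero or downward. The same report could show a patient in the highest QTc category of SAP 8.7.4 with a dose interruption and no matching TEAE.

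**Working it through.** **Inputs from the documents.** Planned n = 60 and exact two-sided 95% intervals (Protocol 8.2, SAP 4); reporting triggers (Protocol 6.3.6); dosing actions (Protocol Table 3); AE rows (SAP 8.7.1). Table 1 schedules ECG, haematology and biochemistry at screening, on day 1 of each cycle and at end of treatment, so all are mandated tests.

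**Step 1: trace an ECG or laboratory deterioration through 6.3.6.**

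| Situation | Result under 6.3.6 |
|---|---|
| Meets an SAE criterion | AE |
| Is the reason for discontinuation | AE |
| Comes with symptoms | The symptom is the AE |
| No symptoms, non-mandated test, clinically relevant | AE |
| No symptoms, mandated test, not serious, drug only held or reduced | No trigger |

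**Step 2: could a hold count as discontinuation?** No. Table 3 uses different actions for the two, and SAP 8.7.1 names interruption and discontinuation separately.

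**Step 3: which findings reach the last row?** The QTc row of Table 3 is the clearest case, because it needs no symptom. A laboratory finding gets there only if it is handled as a Grade 3 or higher adverse reaction, or as unacceptable toxicity, and is then held or reduced without discontinuation. Findings judged to be important medical events are serious and drop out. Appendix A adds that stopping the drug does not by itself make an event important, so a hold alone does not open the SAE route.

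**Step 4: reproduce the plan's intervals.** Lower limit = Beta(0.025; x, 60 − x + 1); upper limit = Beta(0.975; x + 1, 60 − x).

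- x = 0: 0 to 5.96% (plan: 0 to 6.0)
- x = 3: 1.04 to 13.92% (plan: 1.0 to 13.9)

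All nine rows of the plan's table reproduce to within rounding. Those figures are not in dispute.

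**Step 5: size of a possible shortfall.** The documents give no rate for these findings, so the following are assumptions: k = patients with such a finding; r = share recorded as AEs anyway; q = share of the unrecorded who are already counted in that row through another TEAE.

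Shortfall in percentage points = 100 × k × (1 − r) × (1 − q) / 60

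| | k = 1 | k = 2 | k = 3 |
|---|---|---|---|
| r = 0, q = 0 | 1.67 | 3.33 | 5.00 |
| r = 0, q = 0.5 | 0.83 | 1.67 | 2.50 |
| r = 0.5, q = 0.5 | 0.42 | 0.83 | 1.25 |
| r = 1 or q = 1 | 0 | 0 | 0 |

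At the extreme, with three patients, none recorded and none otherwise in the row, a row that should read 3/60 = 5.0% (1.0 to 13.9) would read 0/60 (0 to 6.0).

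**Step 6: what is kept outside the AE tables.** SAP 8.7.2 gives laboratory shift tables and listings of abnormal results. SAP 8.7.4 gives QTc categories by cycle. Protocol 7 requires every interruption and reduction to be entered in the CRF, and the SAP lists drug administration. What is missing is the causality rating, since Protocol 6.3.4 has it made per event ("The Investigator will assess causal relationship between Study drug and each Adverse Event"), and the finding's entry in the AE tables.

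**The case against.** The strongest reply is that 6.3.6 is deliberate. It avoids reporting scheduled test results twice, gives its reason, and the SAP keeps the promise by summarizing those results. It is also the specific recording rule, and it says *only*, whereas 6.1 is a general definition of what an AE can be. The planned dose-modification rows would still have content: symptomatic events, clinical toxicities, serious findings and physical-examination findings. Many investigators might judge a marked QTc prolongation to be an important medical event, which Appendix A says should usually be treated as serious. All of this stands, and it makes the affected group small. It does not explain why a finding that caused discontinuation is reportable while one that caused a hold or reduction is not, in a study that plans to count both.

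A reader might go further in four ways that the documents do not support.

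- *That the AE tables were meant to hold every test-driven hold.* Protocol 8.3 and SAP 8.7.1 plan to count AEs that led to dose changes. They do not say that each such hold is an AE.
- *That the link to dosing is lost because dose action is held only on the AE record.* Protocol 6.3.3 does collect "Action taken with regard to study drug" for each AE, but Protocol 7 puts dose changes in the CRF in any case, and 9.3 lists dose adjustments among the exposure data. Whether the dosing page records a reason cannot be told, because the CRF is not among the documents.
- *That a mismatch could not be found.* AEs, drug administration and abnormal laboratory results are all listed, so it could be found by comparing listings by hand.
- *That the gap matters equally for every scheduled assessment.* The worked cases in the documents are ECG and laboratory findings; Table 3 has no row for vital signs.

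**Conclusion.** The point holds as a minor inconsistency in recording. Under 6.3.6 as written, a symptom-free, non-serious finding on a scheduled ECG or laboratory test that leads only to interruption or reduction is not an AE, and this does not sit with 6.1, Table 3, 8.3 and SAP 8.7.1. The affected rows may be too low or may differ by site. The limit is 1.67 points per affected patient if all 60 planned patients are in the safety set, and zero for a patient already in the row. The total cannot be estimated from the documents and may be zero; the 5-point figure rests wholly on assumed counts. It would go too far to say that the primary outcome is known to be biased or that safety data are lost.

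**What to change.** **Protocol.** Reconcile 6.3.6 with 6.1, Table 3, 8.3 and SAP 8.7.1 by adding to the AE triggers for mandated parameters: *or lead to interruption or reduction of study drug*.

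**SAP.** Add one listing of dose interruptions and reductions with no linked TEAE, shown with the concurrent QTc and laboratory values. It uses data that Protocol 7 and SAP 8.7.2 and 8.7.4 already call for. If patients with QTc of 500 msec or more are also checked against the special-interest table, present that as a screen only. The SAP category is a maximum at or above 500, while Table 3 asks for more than 500 on at least two separate ECGs, so a mismatch does not by itself show an unreported dose-changing finding.

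**Timing.** SAP 8.4 cites a drug dictionary of March 2020, after the planned last visit of 30 June 2019; actual dates are not given. If collection is complete, the protocol wording cannot change what was recorded, but the listing still works.

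**Cost.** One phrase and one listing. The downside is a few more AE entries and slightly higher reported rates. No dose or management rule changes.
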